6 STUDY DESIGN

The planned sample size for this study is 100. In order to evaluate primary, secondary, and safety outcomes, study assessments will be conducted as per the Schedule of Assessments in Section 1.

Virtual

Visit 3

Supplementation Period

Virtual

Visit 4

Visit 5

Visit 2

Figure 1. Study Design

[figure not shown]

Figure 2. Study Schematic

7 SELECTION OF STUDY POPULATION

This study will enroll 100 healthy participants. Each participant must fulfill the inclusion criteria and not meet any of the exclusion criteria as described in Sections 7.1 and 7.2, respectively.

7.1 Inclusion Criteria

- 1. Males and females between 6 and 12 years of age at screening, inclusive
- 2. Children enrolled in and attending school in person at baseline
- 3. Willingness to complete questionnaires, records, and diaries associated with the study and to complete all clinic and remote visits
- 4. A care provider who can reliably bring the participant to study visits. The participant's primary caregiver must be willing and able to complete the questionnaires
- 5. The participant or the participant's parents/guardian are willing and able to provide written assent and/or informed consent as appropriate.
- 6. Agrees to maintain current lifestyle habits (diet, physical activity, medications, supplements, and sleep) as much as possible throughout the study
- 7. Healthy as determined by medical history as assessed by the Qualified Investigator (QI)

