7.2 Exclusion Criteria

- 1. Individuals who are pregnant.
- 2. Allergy, sensitivity, intolerance, or dietary restriction preventing consumption of the investigational product or placebo ingredients
- 3. History or presence of a clinically relevant cardiac, renal, hepatic, endocrine (including diabetes mellitus), respiratory, pulmonary, biliary, metabolic, haematologic, gastrointestinal, or pancreatic disorders, that may affect participation or outcomes as assessed by the QI.
- 4. Confirmed history of COVID-19 infection in the 3 months prior to baseline.
- 5. Immune dysfunction, autoimmune disease, immune compromised and/or taking an immunosuppressive medication, as assessed by the OI
- 6. Severe environmental allergies requiring medical or need for allergy shots, as assessed by the QI.
- 7. Major surgery in the past 3 months or individuals who have planned surgery during the course of the study. Participants with minor surgery will be considered on a case-by-case basis by the QI
- 8. Cancer, except skin basal cell carcinoma completely excised with no chemotherapy or radiation with a follow up that is negative. Volunteers with cancer in full remission for more than five years after diagnosis are acceptable
- 9. Asthma, as assessed by the QI
- 10. Current use of prescribed and/or over-the-counter (OTC) medications, supplements, and/or consumption of food/drinks that may impact the efficacy and or safety of the investigational product (Sections 7.3.1 and 7.3.2)
- 11. Participation in other clinical research studies 30 days prior to baseline, as assessed by the QI
- 12. Participant or participant's caregiver who are cognitively or neurodevelopmentally impaired affecting their ability to give informed consent and/or assent
- 13. Any other condition or lifestyle factor, that, in the opinion of the QI, may adversely affect the participant's ability to complete the study or its measures or pose significant risk to the participant

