9.3 Day 0 (Baseline, Visit 2)

Eligible volunteers will return to the clinic for baseline assessments with collected stool and saliva samples.

Baseline (Day 0) assessments include:

- 1. Review concomitant therapies (inclusive of previous vaccinations) and current health status
- 2. Assess inclusion and exclusion criteria
- 3. Review any pre-emergent AEs
- 4. Urine pregnancy test for potential volunteers that are of child-bearing potential
- 5. Vital sign measurements (BP and HR)
- 6. Weight and height measurements

- 7. Randomization of eligible participants
- 8. Collect blood samples for analysis of: (see Section 9.7.3)
 - a. Quantibody® Human Immune Response Array
 - b. Immunoglobulins A (IgA), G (IgG), E (IgE) and M (IgM) serum levels
- 9. Collect saliva sample for the analysis of Salivary Ig A Levels
- 10. Collect stool samples for microbiome analysis
- 11. Review completed study diaries including CARIFS, Additional respiratory tract symptoms, and GITI symptoms questionnaires
- 12. Dispense investigational product and instruct participants on use
- 13. Dispense study diary inclusive of the CARIFS, Additional respiratory tract symptoms, and GITI symptoms questionnaires
- 14. Dispense stool collection kit for microbiome analysis for Visit 5 (End of Study visit)
- 15. Dispense saliva collection kit for Visit 5 (End of Study visit)

The next visit will be conducted remotely and scheduled for Day 28 (\pm 2 days)

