9.7.7 Canadian Acute Respiratory Illness Flu Scale (CARIFS)

The Canadian Acute Respiratory Illness Flu Scales (CARIFS) is an 18-item questionnaire for children that assesses respiratory illness severity across three domains: symptoms, function and parental impact (**Section 16.2**). Each item is answered on a 4-point scale (no problem = 0, minor problem = 1, moderate problem = 2, major problem = 3), with a higher score denoting a more severe illness (20,21). Participants will complete the CARIFS daily throughout run-in and the study period as part of their study diary. As referenced by *Lazou Ahren et al.* (2020) and *Singh et al.* (2024), incidence, duration, and severity of cold and flu will be defined as the following (21,22):

- *Incidence* will be defined as two or more consecutive days with scores above zero (no problem) in at least two symptoms (headache, sore throat, muscle aches or pain, fever, cough, nasal congestion or runny nose, and vomiting; items 10–16) listed on the CARIFS (21).
- *Duration* will be defined as the length of time from an onset of an incidence (defined above) until the last day with symptoms followed by two days with a 0 score
- Severity will be calculated using two methods. 1) The mean total severity score per day of the individual items per incidence of cold or flu symptoms, and 2) area under the curve (AUC) of daily total symptom scores.

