9.7.8 Gastrointestinal Tract Infection (GITI) Symptoms Questionnaire

Gastrointestinal tract infection (GITI) symptoms will be assessed by completion of the Gastrointestinal tract infection symptoms questionnaire. These questions will completed daily throughout run-in and the study period as part of their study diary. See **Section 16.1** for the questions in this questionnaire.

The GITI symptom questionnaire will comprise the record of the incidence, duration, and severity of individual GITI symptoms. Each item is answered on a 4-point scale (no problem = 0, minor problem = 1, moderate problem = 2, major problem = 3), with a higher score denoting a more severe illness. Participants

will complete the GITI symptom questionnaire daily throughout run-in and the study period as part of their study diary.

Incidence, duration, and severity of GITI symptom will be defined as the following:

- Incidence of a symptom will be defined as the first day with a score of greater than 0
- *Duration of a symptom* will be defined as the length of time from the onset of an incidence (defined above) until the last day the symptom is reported followed by a day with a score of 0
- Severity of a symptom will be calculated using two methods: 1) The mean of the specific symptom scores during the investigational period, and 2) the area under the curve (AUC) of individual symptom scores during the investigational period.

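### The URTI incidence definition does not require onset after the first dose, so read literally a cold carried over from run-in counts as a primary incidence

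*Protocol*

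**What the plan says.** **Incidence definitions.** Protocol 9.7.7 says that a CARIFS incidence "will be defined as two or more consecutive days with scores above zero (no problem) in at least two symptoms", taken from items 10-16. Duration runs from onset to the last symptomatic day that is followed by two zero-score days. For GITI symptoms, 9.7.8 says "Incidence of a symptom will be defined as the first day with a score of greater than 0", and a symptom closes after one zero-score day. Section 9.7.9 applies the same rules to the Additional Respiratory symptoms. All three questionnaires are completed daily in run-in as well as on study.

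**Window and product.** Section 5 sets the primary comparison from baseline to Day 84. Section 8.5 starts product on Day 1.

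**Eligibility.** Inclusion 7 in 7.1 reads "Healthy as determined by medical history as assessed by the Qualified Investigator (QI". The Schedule of Assessments lists medical history at screening only. In 7.2, exclusion 3 reaches "gastrointestinal, or pancreatic disorders, that may affect participation or outcomes as assessed by the QI", and respiratory disorders are in the same list. Exclusion 13 is a catch-all for conditions that, in the QI's opinion, "may adversely affect the participant's ability to complete the study or its measures or pose significant risk to the participant". COVID-19 is the only named infection with an exclusion window.

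**Day 0.** Section 9.3 lists "Review concomitant therapies (inclusive of previous vaccinations) and current health status" as item 1, the eligibility assessment as item 2 and pre-emergent AEs as item 3. Item 7 is "Randomization of eligible participants" and item 11 is "Review completed study diaries including CARIFS, Additional respiratory tract symptoms, and GITI symptoms questionnaires". Section 9.2 describes the 14-day run-in diary but gives it no role in eligibility or in dating onset.

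**The concern.** The primary incidence outcome is meant to show whether the product changes how often children fall ill. An infection already under way before the first dose cannot have been prevented by it. If such an illness is counted, it adds an episode in either arm that treatment could not have averted, and so pulls the rate ratio toward 1. It also adds days to duration and score to AUC. The trial enrols in cold and flu season, so some children will probably be symptomatic on Day 0. The run-in diary records what is needed to identify them, but the protocol does not say to use it.

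A child sampled while ill also has baseline blood and saliva taken during acute illness. Those values are the ANCOVA covariates for the biomarkers, but this touches secondary outcomes only.

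**Working it through.** **1. The definitions applied to one course of illness.** Take a child with symptoms scored above zero every day from Day -3 to Day 5.

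- *CARIFS (cough and runny nose, items 14 and 15).* Days 1 to 5 meet the two-day, two-symptom rule inside the window. Nothing in 9.7.7 asks what came before, so the child scores one primary incidence. The post-baseline days enter duration, and the daily scores enter AUC.
- *GITI or Additional Respiratory symptom.* If the first day above zero is sought from the start of the diary, it is in run-in and outside the baseline-to-Day-84 window. If it is sought from baseline, the symptom scores an incidence at once. The text supports either reading. Mean and AUC are taken over the investigational period, so the post-baseline scores enter those measures either way.

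**2. The plan's own power figure.** Inputs from 11.1: 1.43 placebo and 0.76 active URTI episodes over 84 days, 50 per arm, 20% dropout, two-sided 5%. Completers per arm: 50 x 0.80 = 40.

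Power = Phi( |ln(1.43/0.76)| / sqrt(1/(n x 1.43) + 1/(n x 0.76)) - 1.96 )

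With n = 40: 0.632 / sqrt(1/57.2 + 1/30.4) = 0.632 / 0.2245 = 2.816, and Phi(2.816 - 1.96) = 80.4%. With n = 50 the result is 88.3%. The stated 80% therefore reproduces once dropout is taken off.

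**3. Assumed Day 0 prevalence.** The protocol gives none. Its placebo planning figures imply:

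- if 7.42 is total ill days per child: 7.42/84 = 8.8%, about 4.4 children per arm of 50;
- if 7.42 is days per episode: 1.43 x 7.42/84 = 12.6%, about 6.3 per arm.

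**4. Effect of counting them.** Suppose 1.43 and 0.76 are new episodes only, and every child ill at Day 0 adds one episode. With prevalence p the rates become 1.43 + p and 0.76 + p. Power is at 40 completers per arm.

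| p | Rate ratio | Power | Randomised per arm for 80% |
|---|---|---|---|
| 0 | 0.76/1.43 = 0.531 | 80.4% | 50 |
| 5% | 0.81/1.48 = 0.547 | 78.8% | 53 |
| 8.8% | 0.848/1.518 = 0.559 | 77.5% | 54 |
| 12.6% | 0.886/1.556 = 0.569 | 76.3% | 55 |
| 20% | 0.96/1.63 = 0.589 | 74.0% | 59 |

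At 8.8%-12.6%, carried-over episodes would be 6%-8% of placebo episodes (p divided by 1.43 + p) and 10%-14% of active episodes (p divided by 0.76 + p).

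**The case against.** Four stronger conclusions are tempting, and the protocol does not support them.

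- *That nothing stops an ill child being randomised.* Exclusions 3 and 13 let the QI exclude one, and health status, eligibility and pre-emergent AEs are all listed before randomisation on Day 0. What stands is that this is permission and not a rule. The Introduction (Section 4) explains the respiratory and gastrointestinal exclusion by pre-existing conditions, and a passing cold need not meet either clause.
- *That run-in diaries are reviewed only after randomisation.* This rests on item 11 following item 7. The lists are not declared chronological, and 9.6 lists diary review twice. What stands is that the review has no stated consequence, whenever it happens.
- *That carried-over symptoms count as incidences on all three instruments.* This follows for the CARIFS only. For the other two, the wording is open.
- *That the result is biased.* Carried-over illness is spread over the arms by randomisation, and ordinary chance imbalance is covered by the test's error rate.

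The size can also be challenged, fairly. An episode ending around Day 0 or Day 1 will not give two qualifying days in the window, and QI exclusions would lower the count further. If the cited trial behind the 1.43 counted carried-over episodes, the planning rate already contains them and the power loss need not arise. That source is not at hand.

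Finally, an SAP could settle how episodes that straddle baseline are handled. But the incidence definition is fixed in the protocol, and as written it admits them.

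**Conclusion.** The point holds as a gap in a stated rule. The CARIFS definition counts a URTI carried over from run-in, the GITI and Additional Respiratory definitions leave the question open, no criterion explicitly addresses acute illness at Day 0, and the run-in diary has no stated role.

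The cost is modest: a rate ratio of at most about 0.56-0.57 instead of 0.53, and power of about 76-78% instead of 80.4%. These figures assume that Day 0 prevalence equals the placebo planning burden, that the planning rates are new episodes only, and that nearly every child ill at Day 0 scores an episode. They are therefore toward the upper end at that prevalence. The effect is dilution and noise. It still deserves correction, because the design has no spare power after dropout and the data needed are already collected.

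**What to change.** 1. In 9.7.7-9.7.9, count as primary incidences, with their durations, only those with onset on or after Day 1 that are preceded by the instrument's own closing interval. That is two zero-score days for the CARIFS, and one zero-score day per symptom for GITI and Additional Respiratory symptoms. Use run-in diary days to establish the interval, and report carried-over episodes separately.
2. In 9.3, list run-in diary review before the eligibility assessment and randomisation, so that the QI's Day 0 judgement draws on it.

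The cost is slightly fewer counted events and a little more derivation work. No new data are needed. The counting rule does not remove carried-over scores from AUC, nor does it change baseline samples taken during illness.

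Deferring baseline for a child with an open CARIFS episode is optional. It has a real cost: stool must be collected within 4 days of the visit (9.7.4) and saliva on the day or the day before (9.7.5), so a deferred child may need repeat samples and another visit. It should not be extended unthinkingly to the GITI and Additional Respiratory items, which include passing gas, burping and sneezing and could defer many more children.

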7.2 Exclusion Criteria

- 1. Individuals who are pregnant.
- 2. Allergy, sensitivity, intolerance, or dietary restriction preventing consumption of the investigational product or placebo ingredients
- 3. History or presence of a clinically relevant cardiac, renal, hepatic, endocrine (including diabetes mellitus), respiratory, pulmonary, biliary, metabolic, haematologic, gastrointestinal, or pancreatic disorders, that may affect participation or outcomes as assessed by the QI.
- 4. Confirmed history of COVID-19 infection in the 3 months prior to baseline.
- 5. Immune dysfunction, autoimmune disease, immune compromised and/or taking an immunosuppressive medication, as assessed by the OI
- 6. Severe environmental allergies requiring medical or need for allergy shots, as assessed by the QI.
- 7. Major surgery in the past 3 months or individuals who have planned surgery during the course of the study. Participants with minor surgery will be considered on a case-by-case basis by the QI
- 8. Cancer, except skin basal cell carcinoma completely excised with no chemotherapy or radiation with a follow up that is negative. Volunteers with cancer in full remission for more than five years after diagnosis are acceptable
- 9. Asthma, as assessed by the QI
- 10. Current use of prescribed and/or over-the-counter (OTC) medications, supplements, and/or consumption of food/drinks that may impact the efficacy and or safety of the investigational product (Sections 7.3.1 and 7.3.2)
- 11. Participation in other clinical research studies 30 days prior to baseline, as assessed by the QI
- 12. Participant or participant's caregiver who are cognitively or neurodevelopmentally impaired affecting their ability to give informed consent and/or assent
- 13. Any other condition or lifestyle factor, that, in the opinion of the QI, may adversely affect the participant's ability to complete the study or its measures or pose significant risk to the participant

7.3 Concomitant Medications

Participants who are taking any prescribed medications that are considered not to affect the study outcomes must agree to maintain their current dosing regimen during the study unless otherwise recommended by their general practitioner/nurse practitioner.

7.3.1 Prescribed Medications

Participants on the following concurrent prescribed medications and/or treatments will be excluded during enrollment unless they have been taken off these therapies by their general practitioner/nurse practitioner. In the latter event, the frequency of use and/or dosage may be considered by the QI on a case-by-case basis prior to recommending an appropriate washout or their enrollment in the study.

- 1. Immunomodulators (inc. corticosteroids) such as immunosuppressants or immunostimulants (4 weeks of baseline)
- 2. Cyclosporine, methotrexate, azathioprine, mycophenolate mofetil (1 week of baseline)
- 3. Antibiotics (4 weeks of baseline)

7.3.2 Over-the-counter Medications, Supplements/Natural Health Products, and Food/Drinks

Participants who are currently consuming the following over-the-counter (OTC) medications, supplement and food/drinks will not be allowed to participate unless willing to undergo the specified washout period prior to their baseline visit and agree not to take the supplements during the study. Other OTC supplements and food/drinks will require a case-by-case assessment by the QI based on dose and/or frequency of use to determine adequate washout.

- 1. Other supplements containing the IP (4 weeks of baseline)
- 2. Probiotic Supplements (4 weeks of baseline)
- 3. Natural health products used for cold, flu, or GI health (2 weeks washout)

7.3.3 Washout Periods

Please refer to Section 7.3.2 for washout periods for OTC medications, supplements, and drinks.

7.4 Early Withdrawal

Personal reasons

As stated in the Informed Consent Form (ICF), a participant may withdraw from the study for any reason at any time.

Removal by Qualified Investigator

Participant discontinuation should be considered at the discretion of the Qualified Investigator. The circumstances of any discontinuation must be documented in detail in the participant file and final report. If possible, the evaluations planned for the end of study will be carried out at the time when the participant is withdrawn from the study.

Criteria for removal of participants from the study includes:

Clinical reasons

A participant may be withdrawn from the study if, in the opinion of the Qualified Investigator, it is not in the participant's best interest to continue. Any participant who experiences a serious adverse event (SAE) may be withdrawn from the study at the discretion of the Qualified Investigator. A participant will also be withdrawn due to AEs causing clinically significant illness or the need for prohibited medication(s) during the study. Any participant who becomes pregnant during the course of the study will be withdrawn and followed up with until giving birth.

Protocol violation

Any participant found to have entered this study in violation of the protocol will be discontinued from the study at the discretion of the Qualified Investigator. This will include any participant found to have been inappropriately enrolled (did not meet eligibility criteria). Participant non-compliance includes failure to show up for study visits, failure to take the investigational product as directed, or refusal to undergo study visit procedures. Participants who are found to be taking prohibited medications or supplements without the knowledge of the Qualified Investigator will also be withdrawn. Any major protocol deviations (i.e. those that increase the risk to participants and/or compromise the integrity of the study or its results) will result in participant discontinuation.

Participant Replacement

For all early withdrawals, a participant leaving the study prematurely or in the event of participant removal will NOT be replaced by unless attrition rates are high. It is understood by all concerned that an excessive rate of withdrawals can render the study un-interpretable, thus unnecessary withdrawal of participants should be avoided.

If in the event attrition rates begin to approach 20% and the study sponsor is in agreeance, additional participants may be enrolled at the discretion of the qualified investigator to safeguard study outcomes.

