5 STUDY OBJECTIVES

The objective of this study is to investigate the safety and efficacy of *Bacillus coagulans* SNZ 1969 on the incidence rate, duration, and severity of acute upper respiratory tract infections (URTI) and gastrointestinal tract infection (GITI) symptoms in healthy school-aged children.

Primary outcomes:

- 1. The difference in incidence, duration, and severity (area-under-the-curve (AUC)) of URTI as assessed by the Canadian Acute Respiratory Illness and Flu Scale (CARIFS) from baseline to day 84 between *Bacillus coagulans* SNZ 1969 and placebo
- 2. The difference in incidence, duration, and severity (area-under-the-curve (AUC)) of Additional Respiratory Tract Symptoms as assessed by Additional Respiratory Tract Symptoms questionnare from baseline to day 84 between *Bacillus coagulans* SNZ 1969 and placebo
- 3. The difference in incidence, duration, and severity (AUC) of GITI symptoms as assessed by the GITI Symptoms Questionnaire from baseline to day 84 between *Bacillus coagulans* SNZ 1969 and placebo

Secondary outcomes:

[figure not shown]
- 1. The difference in incidence, duration, and severity (AUC) of URTI as assessed by the CARIFS from baseline to days 28 and 56 between *B coagulans* SNZ 1969 and placebo
- 2. The difference in incidence, duration, and severity (AUC) of Additional Respiratory tract symptoms as assessed by Additional Respiratory Tract Symptoms questionnare from baseline to days 28 and 56 between *B coagulans* SNZ 1969 and placebo
- 3. The difference in incidence, duration, and severity (AUC) of GITI symptoms as assessed by the GITI Symptoms Questionnaire from baseline to days 28 and 56 between *B. coagulans* SNZ 1969 and placebo
- 4. The difference between *B. coagulans* SNZ 1969 and placebo from baseline to days 28, 56, and 84 on:
 - a. Severity of cold/flu and GITI symptoms as assessed by total and individual daily symptom scores
 - b. Number of missed school days
 - c. Number of well days, related to the absence of cold/flu and GITI symptoms
 - d. Use of prescription and non-prescription cold/flu medications to treat cold or flu symptoms
 - e. Total days of illness
- 5. The difference in change between B. coagulans SNZ 1969 and placebo from baseline to day 84 on:
 - a. Saliva secretory immunoglobulin A (sIgA) concentrations
 - b. Serum levels of Immunoglobulin A (IgA), G (IgG), E (IgE) and M (IgM)

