11.2 Analysis Plan

The **Safety Population** will consist of all participants who received any amount of either product, and on whom any post-randomization safety information is available.

The Intention-to-Treat (ITT) Population consists of all participants who are randomized to a study group.

The **Per Protocol (PP) Population** consists of all participants who consumed at least 80% of investigational product or placebo doses, do not have any protocol deviations that affect primary outcomes and complete all study visits and procedures connected with measurement of the primary variable.

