11.3 Statistical Analysis Plan

For both count and continuous primary and secondary outcomes, summary statistics including number of participants, mean, median, standard deviation, first quartile, third quartile, minimum, and maximum will be obtained for each available time interval and for each group. For categorical outcomes, frequencies and percentages will be presented.

The difference in the number of incidences of URTI, duration days of URTI, missed school days, well days, illness days between Bacillus coagulans SNZ 1969 and Placebo groups will be assessed by computing the rate ratio with 95% confidence interval using a generalized linear model with log link function (Poisson or negative binomial regression model).

The difference in the number of incidences of Additional Respiratory Symptoms and the duration days of Additional Respiratory Symptoms between Bacillus coagulans SNZ 1969 and Placebo groups will be assessed by computing the rate ratio with 95% confidence interval using a generalized linear model with log link function (Poisson or negative binomial regression model).

The difference in the number of incidences of GITI symptoms, duration days of GITI symptoms, missed school days, well days, illness days between Bacillus coagulans SNZ 1969 and Placebo groups will be assessed by computing the rate ratio with 95% confidence interval using a generalized linear model with log link function (Poisson or negative binomial regression model).

The difference in the AUC for daily total CARIFS scores, the mean total severity scores of URTI symptoms, the AUC for daily total Additional Respiratory Tract Symptoms questionnaire scores, the AUC of GITI symptom scores, and mean of GITI symptom scores between Bacillus coagulans SNZ 1969 and Placebo groups will be assessed by two-sample t-test if the outcome is normally distributed and Wilcoxon's rank sum test if the outcome is not normally distributed. Normality assumption will be assessed using quantile-quantile (Q-Q) plots.

Fisher's exact test will be used to assess the difference of proportion of participants who used prescription and non-prescription cold/flu medications to treat URTI/GITI symptoms between Bacillus coagulans SNZ 1969 and Placebo. 95% confidence interval of odds ratio will be calculated.

Differences between groups for sIgA, IgA, IgG, IgE, IgM, and immune response biomarkers at day 84 will be assessed by ANCOVA model adjusting for baseline values.

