13.3 Potential Risks and Procedures to Minimize Risk

All potential risks are disclosed to study participants prior to their participation. Potential side-effects of taking the study product may include:

- Abdominal discomfort (such as pain, nausea, changes in bowel habits)
- Dislike of taste
- Worsening of URTI or GITI symptoms

OTC medications for fever, cough etc. can be taken and use is to be documented as part of concomitant medications (see Section 9.7.6). If symptoms persist or worsen, participants will be instructed to contact their heathcare practitioner to ensure that any standard of care treatment can be provided.

Other potential risks associated with this study include venipuncture and the associated risks. Risks associated with venipuncture include pain, bruising, and infection at the site. Alcohol swabs and proper venipuncture procedure will be followed to minimize the risk of infection.

Potential Risks From E-Consent

Participants may receive a link via email/text message to download a PDF copy of the signed consent form. There may be risks of loss of privacy and confidentiality if the PDF copy of this consent form is viewed and/or stored on a personal electronic device (PED), especially if that PED is shared with other users or is lost, hacked, or subject to a search warrant or subpoena. Also, the PDF copy of the consent may not be able to be permanently removed from a PED.

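### Section 7.4 takes children out of the study for significant illness or barred medication without saying the diary continues, so Day 84 primary outcomes may be cut short in the sickest children

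*Protocol*

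**What the plan says.** **Withdrawal.** Protocol Section 7.4 gives, among its clinical reasons for removal: "A participant will also be withdrawn due to AEs causing clinically significant illness or the need for prohibited medication(s) during the study". The wording is mandatory. The same section adds: "If possible, the evaluations planned for the end of study will be carried out at the time when the participant is withdrawn from the study". Section 9.9 refers to an early termination visit. Pregnancy is the only withdrawal for which Section 7.4 describes later follow-up.

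**Which illness and which medication.** Section 10.1.1 defines an adverse event broadly and does not exempt the illnesses the trial measures. Section 13.3 names worsening URTI or GITI symptoms as a possible side effect. Section 7.3.1 lists antibiotics and corticosteroids, but as reasons for exclusion at enrolment. Section 7.3.2 asks families to avoid the listed supplements, including natural products for cold, flu or GI health, during the study. Section 13.3 says: "OTC medications for fever, cough etc. can be taken and use is to be documented as part of concomitant medications". It sends children with persisting or worsening symptoms to their practitioner for standard care. Secondary outcome 4d in Section 5 is: "Use of prescription and non-prescription cold/flu medications to treat cold or flu symptoms".

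**Outcomes and analysis.** Section 5 sets incidence, duration and AUC from baseline to Day 84 as primary. Section 11.1 expresses the CARIFS AUC in score.day. Section 11.3 compares "number of incidences of URTI, duration days of URTI, missed school days, well days, illness days" by a rate ratio from a Poisson or negative binomial model, with no exposure term named, and compares AUC by t-test or Wilcoxon test. Section 11.2 states: "The Intention-to-Treat (ITT) Population consists of all participants who are randomized to a study group".

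**The concern.** The primary outcomes are totals over diary days, and one of the reasons for ending those days is illness of the kind being totalled. A child removed in week three with a bad infection contributes three weeks of symptoms to an 84-day outcome and may look healthier than a classmate with several mild colds who stayed to the end. If the product works, more placebo than active children meet the rule, so more illness is lost from the placebo arm and the estimated effect shrinks. Neither analysis population repairs this: ITT carries the shortened totals and the per-protocol set drops non-completers. The 20% dropout allowance covers lost numbers, not loss related to the outcome. There is also a gap in definition: under Section 9.7.7 a CARIFS episode ends only when two zero-score days follow, so an episode interrupted by withdrawal has no defined end.

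**Working it through.** **Inputs from Section 11.1.** 50 children per arm; 20% dropout; 84 days; placebo 1.43 episodes and 7.42 symptom days; detectable active values 0.76 and 5.80; AUC difference 27.8 with SDs 52.96 and 32.85; effect size 0.63; two-sided 5%; 80% power.

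**Reproducing the plan's figures.** Evaluable per arm: 50 × 0.8 = 40. For a Wald test on the log rate ratio, variance = 1/(n·λ0) + 1/(n·λ1).

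- Episodes: 1/(40 × 1.43) + 1/(40 × 0.76) = 0.0504, SE 0.224. ln(1.43/0.76) = 0.632. 0.632/0.224 − 1.96 = 0.86, power 80.4%.
- Duration days: 1/(40 × 7.42) + 1/(40 × 5.80) = 0.00768, SE 0.0876. ln(7.42/5.80) = 0.246. Power 80.3%.
- AUC: pooled SD = √((52.96² + 32.85²)/2) = 44.07; power 79.4% by t, 80.5% by z. Effect size 0.63 gives 79.5%.

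The stated sample size reproduces: 80/(1 − 0.2) = 100. The planned incidence ratio is 0.76/1.43 = 0.53.

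**What early removal would do.** The protocol gives no trigger rate, so the following is assumed: each episode leads to withdrawal with probability 5%, 10% or 20%; withdrawal comes 3 days after onset; episodes last 7.42/1.43 = 5.2 days in both arms; between-child overdispersion is 0, 0.5 or 1. There were 100,000 simulated children per arm. Ranges run across the overdispersion values.

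| Trigger per episode | Withdrawn, placebo / active | Ratio from unadjusted totals | Ratio with log(observed days) offset | Arm difference in symptom days (about 3.5 if uncut) | Nominal Poisson power, 40 per arm |
|---|---|---|---|---|---|
| 5% | 7% / 4% | 0.54–0.55 | 0.54 | 3.1–3.2 | 75–76% |
| 10% | 13% / 7% | 0.55–0.56 | 0.53–0.55 | 2.7–3.0 | 69–75% |
| 20% | 22–25% / 13–14% | 0.57–0.60 | 0.53–0.57 | 2.1–2.6 | 55–67% |

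If all 50 per arm are counted, nominal power falls from about 88% to 84–85%, 78–83% and 65–77%. The uncut day difference of 3.5 comes from holding episode length equal in both arms. It is not the 7.42 − 5.80 = 1.62 days of Section 11.1, so only its relative shrinkage should be read.

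**Who loses data.** At a 10% trigger without overdispersion, withdrawn placebo children would have had 12.3 symptom days by Day 84; 6.2 are recorded, against 6.7 in the children who stay. With overdispersion 1 the figures are 18.6, 8.9 and 5.9. Either way about half of the withdrawn children's illness is lost.

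**Can analysis alone repair it?** For counts, largely yes if rates are constant and similar between children, less so if children differ: at a 20% trigger and overdispersion 1 the offset ratio is 0.57, not 0.53. For AUC, symptom days stood in for the score (20% trigger, exit two days into an episode). Scaling to 84 days restored the mean difference from 2.5 to 3.5 but raised the placebo SD from 5.9 to 8.5. The standardised difference stayed at about 0.46–0.48, against 0.57 with full follow-up. Scaling reduces bias but recovers no power.

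**The case against.** Several stronger readings are tempting, and the protocol does not support them.

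- **That the protocol ends the diary and compares raw sums.** It says neither. That diaries stop is an inference from removal from the study and the early end-of-study evaluations. A rate ratio is compatible with an exposure offset, and naming the offset or a scaling for AUC is ordinary analysis-plan content. This stands. What remains in the protocol itself is whether the days are collected.
- **That any child given an antibiotic must leave.** The Section 7.3.1 list governs enrolment, no on-study list of barred prescriptions is given, and Section 13.3 allows OTC treatment. Ordinary colds need not trigger removal. Whether URTI or GITI counts as a withdrawing adverse event is unclear, not settled.
- **That 7.4 contradicts outcome 4d.** It is a tension. Use before withdrawal is still counted, and the planned test concerns the proportion of users.
- **That ITT is not really ITT.** The set includes everyone randomised; the weakness is shortened follow-up within it.
- **That the rule could manufacture a benefit.** With no product effect, illness-driven withdrawal is equal between arms. A spurious ratio needs unequal dropout for other reasons. For example, 30% versus 10% leaving at mean Day 42 gives (1 − 0.30 × 0.5)/(1 − 0.10 × 0.5) = 0.895. Nothing in the protocol suggests such an imbalance.

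The 20% trigger is also severe: it implies 22–25% placebo withdrawal from illness alone, above the 20% allowed for all dropout. Section 7.4 itself says unnecessary withdrawals should be avoided.

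**Conclusion.** The point holds in limited form. Section 7.4 ties leaving the study to illness that may be the outcome, describes no further diary collection, and does so while the primary counts, days and AUC run to Day 84. Under assumed triggers of 5% to 20% of episodes, the incidence ratio moves from about 0.53 to 0.54–0.60, a modest pull toward no difference. The power loss ranges from small to substantial, down to 55% at the extreme. These sizes rest on assumed trigger rates, timing and overdispersion, and on unadjusted totals for the ratio; only the direction is secure. The lasting harm is that uncollected diary days cannot be recovered by any later analysis. It should be fixed; confidence is moderate.

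**What to change.** 1. Amend Section 7.4 to separate stopping product from leaving the study. State that the daily diary continues to Day 84 after product is stopped, unless consent or assent is withdrawn. This is the main remedy.
2. State that all randomised children are analysed on all diary days collected, including days after product is stopped.
3. For children who still leave early, use log(observed diary days) as the offset for counts and day totals, and do not compare unscaled AUC totals. Scaling AUC to observed days reduces bias but is no substitute for collecting the days.
4. Reconcile Sections 5 (outcome 4d), 7.3.1, 7.3.2, 7.4 and 13.3 on which on-study medication use or outcome illness leads to withdrawal. That content is a clinical decision for the sponsor and the investigator; no rule is proposed here, and the criteria for stopping product need not change.

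Cost: a short amendment to 7.4 and some wording in 11.3. Some families would keep filling in the diary after stopping product. No visits are added.
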